## **6 STUDY INTERVENTION**

Study intervention is defined as any investigational intervention(s), marketed product(s), placebo, or medical device(s) intended to be administered to a study participant according to the study protocol.

Clinical supplies (HBVAXPRO™) will be packaged to support enrollment. Clinical supplies will be affixed with a clinical label in accordance with regulatory requirements.

### **6.1 Study Intervention(s) Administered**

The study intervention to be used in this study is outlined in [Table 1](#).

Table 1 Study Intervention

Arm Name	Arm Type	Intervention Name	Intervention Type	Dose Formulation	Unit Dose Strength	Dosage Level	Route of Admin.	Vaccination Regimen	Use	IMP/NIMP	Sourcing
1	Experimental	HBVAXPRO™	Biological/ Vaccine	Sterile Suspension (Prefilled Syringe)	Refer to Product labeling	0.5 mL	IM	Single dose on Day 1	Challenge Agent	NIMP	Central

admin. = administration; IMP = investigational medicinal product; NIMP = non-investigational medicinal product

The classification of IMP and NIMP in this table is based on guidance issued by the European Commission and applies to countries in the European Economic Area (EEA). Country differences with respect to the definition/classification of IMP/NIMP may exist. In these circumstances, local legislation is followed.

All supplies indicated in **Table 1** will be provided per the "Sourcing" column depending upon local country operational requirements. If local sourcing, every attempt should be made to source these supplies from a single lot/batch number where possible (eg, not applicable in the case where multiple lots or batches may be required due to the length of the study, etc.).

Refer to Section 8.1.8 for details regarding administration of the study intervention.

## **6.2 Preparation/Handling/Storage/Accountability**

### **6.2.1 Dose Preparation**

There are no specific calculations or evaluations required to be performed in order to administer the proper dose to each participant. The rationale for selection of doses to be used in this study is provided in Section 4.3.

### **6.2.2 Handling, Storage, and Accountability**

The investigator or designee must confirm appropriate temperature conditions have been maintained during transit for all study intervention received, and any discrepancies are reported and resolved before use of the study intervention.

Only participants enrolled in the study may receive study intervention, and only authorized site staff may supply or administer study intervention. All study interventions must be stored in a secure, environmentally controlled, and monitored (manual or automated) area in accordance with the labeled storage conditions with access limited to the investigator and authorized site staff.

The investigator, institution, or the head of the medical institution (where applicable) is responsible for study intervention accountability, reconciliation, and record maintenance (ie, receipt, reconciliation, and final disposition records).

For all study sites, the local country Sponsor personnel or designee will provide appropriate documentation that must be completed for drug accountability and return, or local discard and destruction if appropriate. Where local discard and destruction is appropriate, the investigator is responsible for ensuring that a local discard/destruction procedure is documented.

The study site is responsible for recording the lot number, manufacturer, and expiry date for any locally purchased product (if applicable) as per local guidelines unless otherwise instructed by the Sponsor.

The investigator shall take responsibility for and shall take all steps to maintain appropriate records and ensure appropriate supply, storage, handling, distribution, and usage of study interventions in accordance with the protocol and any applicable laws and regulations.

### **6.3 Measures to Minimize Bias: Randomization and Blinding**

#### **6.3.1 Intervention Assignment**

Participants in this study will be allocated by nonrandom assignment.

#### **6.3.2 Stratification**

No stratification based on age, sex, or other characteristics will be used in this study.

#### **6.3.3 Blinding**

This is an open-label study; therefore, the Sponsor, investigator, and participant will know the vaccine administered.

### **6.4 Study Intervention Compliance**

Participants will receive single-dose of HBVAXPRO™ administered at the study site. The date and time of administration will be recorded in the source document and in the eCRF.

### **6.5 Concomitant Therapy**

Medications or vaccinations specifically prohibited in the exclusion criteria are not allowed during the ongoing study (see Section 5.2 for details). Systemic steroids  $\geq 20$  mg/day for  $\geq 5$  consecutive days are prohibited through the course of the study.

If there is a clinical indication for any medications or vaccinations specifically prohibited, the investigator should discuss any questions regarding this with the Sponsor Clinical Director. The final decision on any supportive therapy or vaccination rests with the investigator and/or the participant's primary physician. However, the decision to continue the participant in the study requires the mutual agreement of the investigator, the Sponsor, and the participant or the participant's legally acceptable representative.

If a medical condition requires the use of a prohibited steroid regimen, immunoglobulin, blood, or blood products during a participant's participation in this study, one of the individuals listed on the Sponsor Contact Information page must be notified as soon as possible. Any concurrent medication or medical treatment must be recorded on the appropriate eCRF.

No other investigational compound or device may be administered at any time during this study without prior approval by the Sponsor.

#### **6.5.1 Rescue Medications and Supportive Care**

No rescue or supportive medications are specified for use in this study.

## **6.6 Dose Modification (Escalation/Titration/Other)**

No dose modification is allowed in this study.

## **6.7 Intervention After the End of the Study**

There is no study-specified intervention following the end of the study.

## **6.8 Clinical Supplies Disclosure**

This study is open-label; therefore, the participant, the study site personnel, the Sponsor, and/or designee are not blinded. Study intervention (name, strength, or potency) is included in the label text; random code/disclosure envelopes or lists are not provided.

# **7 DISCONTINUATION OF STUDY INTERVENTION AND PARTICIPANT WITHDRAWAL**

## **7.1 Discontinuation of Study Intervention**

In clinical studies with a single intervention, discontinuation of study intervention can only occur prior to the intervention and generally represents withdrawal from the study.

Participants who receive a single-dose intervention cannot discontinue study intervention.

## **7.2 Participant Withdrawal From the Study**

A participant must be withdrawn from the study if the participant or participant's legally acceptable representative withdraws consent from the study.

If a participant withdraws from the study, they will no longer receive study intervention or be followed at scheduled protocol visits.

Specific details regarding procedures to be performed at the time of withdrawal from the study, are outlined in Section 8.1.9. The procedures to be performed should a participant repeatedly fail to return for scheduled visits and/or if the study site is unable to contact the participant are outlined in Section 7.3.

## **7.3 Lost to Follow-up**

If a participant fails to return to the clinic for a required study visit and/or if the site is unable to contact the participant, the following procedures are to be performed:

- The site must attempt to contact the participant and reschedule the missed visit. If the participant is contacted, the participant should be counseled on the importance of maintaining the protocol-specified visit schedule.

- The investigator or designee must make every effort to regain contact with the participant at each missed visit (eg, telephone calls and/or a certified letter to the participant's last known mailing address or locally equivalent methods). These contact attempts should be documented in the participant's medical record.
- Note: A participant is not considered lost to follow-up until the last scheduled visit for the individual participant. The missing data for the participant will be managed via the prespecified statistical data handling and analysis guidelines.

## 8 STUDY ASSESSMENTS AND PROCEDURES

- Study procedures and their timing are summarized in the SoA.
- Adherence to the study design requirements, including those specified in the SoA, is essential and required for study conduct.
- The investigator is responsible for ensuring that procedures are conducted by appropriately qualified (by education, training, and experience) staff. Delegation of study site personnel responsibilities will be documented in the Investigator Trial File Binder (or equivalent).
- All study-related medical decisions must be made by an investigator who is a qualified physician.
- All screening evaluations must be completed and reviewed to confirm that potential participants meet all eligibility criteria. The investigator will maintain a screening log to record details of all participants screened and to confirm eligibility or record reasons for screening failure, as applicable.
- Procedures conducted as part of the participant's routine clinical management (eg, blood count) and obtained before signing of ICF may be utilized for screening or baseline purposes provided the procedure met the protocol-specified criteria and were performed within the time frame defined in the SoA.
- Additional evaluations/testing may be deemed necessary by the investigator and or the Sponsor for reasons related to participant safety. In some cases, such evaluation/testing may be potentially sensitive in nature (eg, HIV, Hepatitis C), and thus local regulations may require that additional informed consent, and assent if applicable, be obtained from the participant. In these cases, such evaluations/testing will be performed in accordance with those regulations.

The maximum amount of blood collected from each participant over the duration of the study will not exceed 7 mL (3.5 mL at each of Visits 1 and 2).

Repeat or unscheduled samples may be taken for safety reasons or for technical issues with the samples.

## **8.1 Administrative and General Procedures**

### **8.1.1 Informed Consent/Assent**

The investigator or medically qualified designee (consistent with local requirements) must obtain documented consent, and assent if applicable, from each potential participant or each participant's legally acceptable representative prior to participating in a clinical study. If there are changes to the participant's status during the study (eg, health or age of majority requirements), the investigator or medically qualified designee must ensure the appropriate consent/assent is in place.

#### **8.1.1.1 General Informed Consent/Assent**

Consent/assent must be documented by the participant's dated signature or by the participant's legally acceptable representative's dated signature on a consent/assent form along with the dated signature of the person conducting the consent discussion.

A copy of the signed and dated consent/assent form should be given to the participant before participation in the study.

The initial informed consent/assent form, any subsequent revised written informed consent/assent form, and any written information provided to the participant must receive the IRB/IEC's approval/favorable opinion in advance of use. The participant or his/her legally acceptable representative should be informed in a timely manner if new information becomes available that may be relevant to the participant's willingness to continue participation in the study. The communication of this information will be provided and documented via a revised consent/assent form or addendum to the original consent/assent form that captures the participant's dated signature or by the participant's legally acceptable representative's dated signature.

Specifics about a study and the study population will be added to the consent/assent form template at the protocol level.

The informed consent will adhere to IRB/IEC requirements, applicable laws and regulations, and Sponsor requirements. The assent, as applicable, will adhere to IRB/IEC requirements, applicable laws and regulations and Sponsor requirements.

### **8.1.2 Inclusion/Exclusion Criteria**

All inclusion and exclusion criteria will be reviewed by the investigator, who is a qualified physician, to ensure that the participant qualifies for the study. The investigator should consult with the Sponsor's Clinical Director for any questions about participant eligibility.

### **8.1.3 Participant Identification Card**

All participants will be given a participant identification card identifying them as participants in a research study. The card will contain study site contact information (including direct telephone numbers) to be used in the event of an emergency. The investigator or qualified designee will provide the participant with a participant identification card immediately after the participant provides written informed consent/assent. At the time of intervention allocation, site personnel will add the treatment/allocation number to the participant identification card.

The participant identification card also contains contact information for the emergency unblinding call center so that a healthcare provider can obtain information about study intervention in emergency situations where the investigator is not available.

### **8.1.4 Medical History**

The participant's medical history for the 5 years prior to Visit 1 (Day 1) will be obtained by the investigator or qualified designee at Visit 1 (Day 1) before vaccination.

### **8.1.5 Prior and Concomitant Medications Review**

#### **8.1.5.1 Prior Medications**

The collection of previous medications and vaccinations (within the 30 days prior to Visit 1/Day 1) will be limited to the not allowed medications and vaccinations that should have led to the participant's ineligibility (see Section 5.2); these medications and vaccinations, if any, should be recorded in the eCRF.

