### Prior/Concomitant Therapy

7. Has received any hepatitis B vaccine after participation in Protocol V419-007 or V419-008.

8. \*Is receiving immunosuppressive therapy, including chemotherapeutic agents used to treat cancer or other conditions, and interventions associated with organ or bone marrow transplantation, or autoimmune disease.
9. \*Meets one or more of the following systemic steroid exclusion criteria:
  - a. Has received any dose of systemic steroids within 7 days prior to entering study.
  - b. Is expected to require systemic steroids  $\geq 20$  mg/day for  $\geq 5$  consecutive days through the course of the participant's participation in the study.

Note: Topical, ophthalmic, intra-articular or soft-tissue (eg, bursa, tendon steroid injections), and inhaled/nebulized steroids are permitted.

10. \*Has received any licensed, non-live vaccine within the 14 days before receipt of study vaccine or is scheduled to receive any licensed, non-live vaccine within 30 days following receipt of any study vaccine. **Exception:** Inactivated influenza vaccine may be administered but must be given at least 7 days before receipt of any study vaccine or at least 15 days after receipt of any study vaccine.
11. \*Has received any licensed live vaccine within 30 days before receipt of study vaccine or is scheduled to receive any live vaccine within 30 days following receipt of any study vaccine.
12. \*Has received a blood transfusion or blood products, including immunoglobulins within the 6 months before receipt of study vaccine or is scheduled to receive a blood transfusion or blood product within 30 days of receipt of study vaccine. Autologous blood transfusions are not considered an exclusion criterion.

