### **Prior/Concurrent Clinical Study Experience**

13. \*Has participated in another clinical study of an investigational product within 2 months before study vaccination at Visit 1 (Day 1) or plans to participate anytime during the duration of the current clinical study. Participants enrolled in observational studies may be included; these will be reviewed on a case-by-case basis for approval by the Sponsor.

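### Does the 30-day recording window for disallowed prior products let an interim hepatitis B dose slip into the primary analysis?

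*Combined protocol and SAP*

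**What the plan says.** Section 8.1.5.1 states: "The collection of previous medications and vaccinations (within the 30 days prior to Visit 1/Day 1) will be limited to the not allowed medications". It covers vaccinations as well, and it describes the items to be entered as those "that should have led to the participant's ineligibility (see Section 5.2").

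The Section 5.2 criteria it points to have different look-backs. Exclusion 11 matches the window: "Has received any licensed live vaccine within 30 days before receipt of study vaccine". Three others run longer:

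- Exclusion 7: "Has received any hepatitis B vaccine after participation in Protocol V419-007 or V419-008".
- Exclusion 12: "Has received a blood transfusion or blood products, including immunoglobulins within the 6 months before receipt of study vaccine".
- Exclusion 13: "Has participated in another clinical study of an investigational product within 2 months before study vaccination at Visit 1 (Day 1").

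Eligibility itself is handled elsewhere. Section 8.1.2 says: "All inclusion and exclusion criteria will be reviewed by the investigator, who is a qualified physician". In the Section 1.3 schedule, the inclusion/exclusion row sits under screening, and its note makes a review of earlier medications and vaccinations at Visit 1 part of deciding eligibility, with no time limit. The prior and concomitant medication review is a separate row under post-enrollment procedures. Section 8.1.4 adds: "The participant's medical history for the 5 years prior to Visit 1 (Day 1) will be obtained by the investigator or qualified designee".

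**The concern.** Section 8.1.5.1 exists to capture products that should have kept a child out, yet its window is too short for three of the criteria that define such products. Exclusion 7 matters most. The study has one group, the primary analysis is per-protocol, and the result is to be read as durability of Vaxelis about 9 years on. A child given another hepatitis B vaccine in between would probably have a higher Day 1 level and respond on Day 30 for a reason other than Vaxelis. Both the primary proportion and the Day 1 GMC would be pushed upwards.

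Section 9.5.1 lists receipt of a prohibited vaccine before study vaccination as a possible ground for per-protocol exclusion. If the only specified record of such products stops at 30 days, that exclusion seems to lack the data it needs.

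**Working it through.** **1. Look-backs against the 30-day window** (Section 5.2; months and years converted to days)

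| Exclusion | Look-back | Share inside 30 days |
|---|---|---|
| 9a, systemic steroids | 7 days | all |
| 10, non-live vaccine | 14 days (7 for inactivated influenza) | all |
| 11, live vaccine | 30 days | all |
| 13, other investigational study | 2 months, about 60.9 days | 30/60.9 = 49% |
| 12, blood products | 6 months, about 182.6 days | 30/182.6 = 16% |
| 7, hepatitis B vaccine | about 9 years, 9 × 365.25 = 3,287 days | 30/3,287 = 0.9% |

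The mismatch is real. Exclusion 13 is a poor example, because it concerns taking part in a study and is not naturally a medication or vaccination entry. For exclusion 12, the medical history reaches back 5 years, and 5/0.5 = 10 times the look-back, so a transfusion or immunoglobulin may well appear there. For exclusion 7 the history falls short: children aged 8 to 10 had the toddler dose at 11 to 12 months of age, about 7 to 10 years earlier, which leaves 2 to 5 years outside it.

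**2. What happens to an interim hepatitis B dose older than 30 days**

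- *Reported at Visit 1.* The eligibility review has no time limit, exclusion 7 applies, and Section 5 allows no waivers. Exclusion 7 has no asterisk, so the visit cannot simply be rescheduled. The child is a screen failure, entered in the screening log (Section 8) with the screen-failure details required by Section 5.4.
- *Learned of after enrollment.* Section 9.5.1 sets no time limit and does not depend on the Section 8.1.5.1 entry. The child can be excluded from the per-protocol population.
- *Never reported.* There is nothing to record under a window of any length.

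In none of the three cases does the length of the window decide who is analysed.

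**3. Size of the third case**

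The plan's yardstick first. Section 9.9.1 states a half-width of 4.0 points for 200 children at 95%. The Clopper-Pearson interval for 190/200 is 91.0% to 97.6%. The distance from 95% to the lower limit is 4.0 points, which is the stated figure; half the full width is 3.29.

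The documents give no rate of interim doses and no titre ratio, so these inputs are assumptions: a fraction c = 1% to 5% with an unreported dose, all of them responding, and Day 1 levels f = 10 to 30 times higher in those children.

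Rise in the primary rate = c × (1 − p), where p is the response rate in the other children:

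- p = 95%: 0.01 × 0.05 = 0.05 points, to 0.05 × 0.05 = 0.25 points. In children, 200 × c × (1 − p) = 0.1 to 0.5.
- p = 85%, the lowest rate in Table 3: 0.01 × 0.15 = 0.15 points, to 0.05 × 0.15 = 0.75 points.
- Against 4.0 points, the rise at p = 95% is 0.05/4.0 = 1% to 0.25/4.0 = 6%. Against 3.29, the upper figure is 0.25/3.29 = 8%.
- A 1-point rise at p = 95% needs c = 0.01/0.05 = 20%.

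Day 1 GMC ratio = f^c:

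- c = 1%: 10^0.01 = 1.023 and 30^0.01 = 1.035.
- c = 5%: 10^0.05 = 1.122 and 30^0.05 = 1.185.

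All of these figures describe unreported doses. The share that a longer recording window would remove is zero.

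**The case for a change.** The strongest reply is that the listed safeguards name no source. Neither the physician's review nor the schedule says how a site establishes that a child had no hepatitis B vaccine over 7 to 10 years. Section 4.1 refers readers to Section 8 for procedural detail, and the only prior-product window given there is 30 days. Checking the vaccination record would be cheap, would need no extra visit or blood sample, and is the one step that could find an unreported dose. The Day 1 GMC could also be off by 12% to 19% at 5% exposure.

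Part of this stands. The windows do not match, no passage names a vaccination-record check, and a child enrolled in error whose older dose comes to light later has no entry under Section 8.1.5.1.

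The rest does not lead to a change. A record check is a different matter from the recording window: it specifies how sites verify a criterion they must already verify. Section 10.1.9 foresees requests for earlier medical records and requires current ones to be available. Section 10.1.8 leaves data management procedures to separate documents, so the absence of a field for hepatitis B vaccine history cannot be inferred from the protocol. The GMC figure needs 10 of 200 children to have had an unreported dose, plus an assumed titre ratio, whereas Section 2.1 describes further doses as neither needed nor advised.

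**Conclusion.** No change to the plan follows. Section 8.1.5.1 is worded more narrowly than the criteria it cites, but the mismatch affects only where a breach is written down. Exclusion 7 is reviewed without a time limit, and a breach that becomes known leads to a screen failure or can be removed under Section 9.5.1. What remains is a missing prior-product entry for a child enrolled in error, which the deviation handling in Section 9.5.1 can still cover.

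The window shifts no estimate. Unreported doses could shift the primary rate by 0.05 to 0.25 points at 95% response and by at most 0.75 points at 85%, and could raise the Day 1 GMC by 2% to 19%. These ranges assume 1% to 5% exposure, full response and a 10- to 30-fold titre difference, none of which the documents supply. Section 2.1 points to the low end, and a wider window would not reduce any of these figures. The conclusion rests on sites carrying out the eligibility review that Sections 1.3 and 8.1.2 require.
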